## LIST OF ABBREVIATIONS

AD	Atopic Dermatitis
CBT	Cognitive-behavioral therapy
PROMIS	Patient-Reported Outcomes Measurement Information Systems
IRB	Institutional Review Board
PRO	Patient Reported Outcomes
QOL	Quality of life
PSC-C	Pain Catastrophization Scale for Children adapted for itch
PIQ-C	PROMIS Itch Questionnaire-Children
CDLQI	Children’s Dermatology Life Quality Index
NRS	Numeric Rating Scale
POEM	Patient Orientated Eczema Measure

## 1.0 Objectives

Chronic itch is one of the most difficult to treat symptoms in atopic dermatitis (AD; eczema). Many children with eczema suffer from a chronic focus (rumination) on itch. Cognitive Behavioral Therapy (CBT) intervention is effective in treating rumination on pain in other chronic diseases, and would likely be successful to treat itch in eczema. In this project we will develop an “Itch CBT” intervention specific for itch rumination in eczema. After developing a standard protocol based on input from patients, parents, clinicians and the National Eczema Association, we will then pilot the intervention in our multidisciplinary eczema clinic. The total intervention will last approximately one month. The intervention will consist of four 60-minute telehealth sessions with children and their parent/guardian. The first visit will be done ~60 directly after a telehealth clinic visit to assess areas of difficulty followed by 3 weekly telehealth visits to assess progress and implementation, provide further instruction, and review as necessary. At each time-point, we will assess how much the intervention decreased itch, improved medication adherence, and improved other quality of life concerns (anxiety, depression, sleep, and stigma). Future directions will include making the Itch CBT protocol widely available and securing an NIH grant to broadly test the efficacy.

## 2.0 Background

Eczema is characterized by chronic itch. Many children develop a chronic focus (rumination) on their itch. Rumination is a maladaptive method of responding to distress, in which the individual thinks obsessively about the source of distress, its possible causes and correlates. The rumination on chronic itch in eczema can have detrimental effects on one’s quality of life, as well as induce significant anxiety about when itch will return, how long it will last, and how it will affect physical and social functioning.

Cognitive-behavioral therapy (CBT) is a frontline treatment for rumination, as it focuses on teaching strategies so that the individual can examine distressing thoughts objectively and determine their validity, replace negative thinking patterns with more adaptive thought patterns, and increase the individual’s awareness to their problematic thought patterns. Additionally, CBT helps the individual to implement behavioral strategies to cope with possibly anxiety-inducing situations, such as scratching while trying to go to sleep. Through behavioral strategies, such as mindfulness and meditation activities, exposure, or distraction, the individual can learn to function in spite of their physical symptoms and cope more effectively.

We propose to create a protocol for Itch CBT that focuses on itch rumination and anxiety in eczema for children ages 8-17 years. We hypothesize that an Itch CBT intervention is an effective, non-medication based, easy to implement strategy to improve itch in children with eczema. Our first aim was to develop an Itch CBT protocol specific for children with eczema. With the input of children with eczema and their families as to the nature of their symptom-related distress, we created a brief intervention and questionnaire to measure itch-related distress and rumination and a set of cognitive,

## Brief Cognitive Behavioral Therapy to Treat Itch Rumination “Itch CBT” in Eczema

behavioral, and relaxation strategies to combat itch rumination. With expert input from the National Eczema Association and our research team, we have formalized a protocol for Itch CBT. In our second aim, we will pilot the protocol in a brief (4 session) intervention as part of an interdisciplinary AD clinic, comparing Itch CBT to usual care (our standard educational handouts).

Because each group will have similar levels of eczema severity and will be receiving the same level of medical care, we will be able to attribute changes over time between the two groups to this mental health intervention. We predict that patients treated with Itch CBT will show significantly less itch and less severe itch, as well as significantly greater quality of life, at follow-up compared to those receiving standard treatment. Predicted secondary outcomes include decreased rumination on itch, sleep disturbance, depression, and anxiety, as well as improved medication adherence, and social/family functioning. This pilot study will allow us to measure itch rumination, its effects on children with AD, and the efficacy of Itch CBT in itch rumination. With this preliminary data, we can apply for NIH funding to provide more extensive evidence for the efficacy of Itch CBT in treating itch rumination; ideally we hope to develop an Itch CBT protocol that can easily be implemented by trained personnel in the clinic setting or even as an online tool for patients. The National Eczema Association is the perfect partner for our research team to help develop and disseminate this intervention.

### 3.0 Hypothesis and Specific Aims

**Hypothesis:** Our overall hypothesis is that a brief CBT intervention to treat itch rumination is an effective adjunctive strategy to improve itch in AD.

**Aim 1:** Develop and refine a brief, user-friendly, easily deployable CBT intervention to treat itch rumination (Itch CBT) for pediatric AD. We will conduct semi-structured interviews of 20 patient/parent dyads to tailor a CBT rumination intervention for itch in AD to determine the best cognitive and behavioral strategies to implement in Itch CBT. Both open- and close-ended questioning will be used to allow for patient suggestions for new material, as well as input on proposed materials and strategies.

**Aim 2:** Determine the efficacy of the itch rumination intervention in reducing distress related to AD and itch, as well as correlates of AD that affect quality of life, such as social concerns and sleep disturbance. Preliminary data will also be collected to determine the validity of a child and parent-proxy questionnaire designed to measure rumination on itch in AD.

### 4.0 Inclusion and Exclusion Criteria

#### 4.1 Inclusion Criteria:

1. Moderate to severe atopic dermatitis [assessed by Patient Oriented Eczema Measure (POEM) score of >-8 OR NRS itch score of >= 4].

## Brief Cognitive Behavioral Therapy to Treat Itch Rumination “Itch CBT” in Eczema

2. English speaking (restriction of PROMIS measure).
3. Age 8-17 years.
4. Currently receiving treatment at Lurie Children’s Hospital for atopic dermatitis.
5. Parent or guardian available to participate in protocol.
6. For Aim 2, Have sufficient technology (e.g., cell phone, computer, tablet, etc.) that can be used to access Zoom conference technology for telemedicine visits.

[figure not shown]
### 4.2 Exclusion Criteria:

1. Inability to comprehend and complete questionnaires.
2. History of intellectual disability or psychosis.
3. For Aim 2, enrollment in Aim 1.

## 5.0 Procedures Involved

### 5.1 Overall Study Design

The overall study design is to develop a brief CBT intervention tailored to itch rumination via qualitative methods, including creating an interview guide with closed- and open-ended questions for stakeholders concerning itch-related distress and rumination. From these interviews, the itch rumination CBT will be created to address common fears and anxiety around itch, ruminative thoughts concerning itch, and other correlates associated with lowered quality of life in AD. This intervention will then be tested in a pilot RCT to compare the brief CBT intervention to usual care. Although therapists will not be blinded to intervention group, the research assistant assessing and analyzing outcomes with patients and their caregiver will be blinded to which intervention they received. Figure 1 summarizes our interventional model of CBT Itch.

Target Population: A convenience sample of children (8-17 years) with moderate-severe AD (and one parent) will be recruited from our group’s multidisciplinary AD clinic.

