**Randomization Procedures:** Participants will be randomized to one of two groups: (1) Itch CBT or (2) Usual care. Randomization will occur on a 1:1 ratio and within strata, which are gender (male vs. female) and Itch Numerical Rating Scale (4-6 vs. 7-10). Participants will be randomized to treatment based on a predetermined list within each strata created using the *blockrand* package of R. Randomization will occur by blocks, with varying block sizes, in accord with recommended methods for RCTs. The randomization key will be linked to a unique study ID number, as well as to a treatment condition (Itch CBT vs. Usual Care). Participants will be aware that there are different arms they can be assigned to and will know which randomization group they are assigned.

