## Brief Cognitive Behavioral Therapy to Treat Itch Rumination “Itch CBT” in Eczema

cope with itch, social concerns, mood and anxiety concerns related to AD, sleep concerns, and areas of functional impairment due to AD.

Following their assessment, families will be instructed on how to download a free version of the Zoom application onto their internet-capable personal device, with specific details on how to connect for follow-up telehealth visits. Resources will be provided to families for technical support. Therapists will then follow up with participants for three sessions on a weekly basis via telehealth on Northwestern Zoom, which is encrypted to increase security and privacy. Sessions will include instruction on mindfulness-based activities, behavioral interventions to improve adherence, action planning during flares, and coping mechanisms to help cope with social challenges (see CBT Supplemental Materials). Participants will review the session with their parents, in conjunction with their therapist, and be given homework to complete for the following week. Following each therapy session, participants will complete study surveys via REDcap and at 4 weeks following the intervention. Participants will have up to 2 weeks to complete the follow-up questionnaires.

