## Brief Cognitive Behavioral Therapy to Treat Itch Rumination “Itch CBT” in Eczema

Parent Proxy Pediatric Itch – Short Form 1 (2+6)	X	X	X	X	X
PROMIS Parent Proxy – Anxiety & Depression	X			X	X
PROMIS Parent Proxy—Positive Affect	X			X	X
PROMIS Sleep - Parent	X			X	X
VAS Dose	X	X	X	X	X
Itch Severity VAS	X	X	X	X	X
Five Facet Mindfulness Questionnaire SF	X			X	X
PROMIS Family Relationships	X			X	X

### 5.4 Statistical Analysis Plan – Aim 2

Because this a clinical trial, our primary statistical approach will be a response profile analysis. In this model, the effect of treatment and other variables are used predict the outcome over time, but an influence of treatment is not posited for pre-treatment assessments. This method is recommended for analyzing clinical trials. We will include participants using the intent-to-treat criterion, in which all randomized participants are included in the analysis. All aspects of this clinical trial will be reported in accord with CONSORT guidelines. Although the response profile analysis will be our primary approach, we will also explore alternative approaches. Latent growth curve models use all available data (i.e., they do not discard observations with missing data) and provide valid inferences in the presence of missing outcome data under the missing at random (MAR) assumption.

The primary outcome measures will be the NRS Itch Severity and the CDLQI. All other questionnaires will be used as secondary outcome measures.

Primary outcomes:

1. NRS Itch Severity

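### Blinding the research assistant does not blind the ratings, which come from families who know their arm, and only the CBT arm completes its visit surveys following a therapy session

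*Combined protocol and SAP*

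**What the plan says.** Section 5.1 (Overall Study Design) describes the blinding in one sentence. It begins "Although therapists will not be blinded to intervention group" and goes on to say that "the research assistant assessing and analyzing outcomes with patients and their caregiver will be blinded to which intervention they received". No other blinding measure is described.

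Section 5.3 (Randomization Procedures) says that participants "will know which randomization group they are assigned".

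Section 5.4 says "The primary outcome measures will be the NRS Itch Severity and the CDLQI" and "All other questionnaires will be used as secondary outcome measures". The Tables of Assessments list 12 instruments for children and 9 for parents. All are questionnaires or rating scales, and no clinician-rated or objective measure is listed.

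On timing in the CBT arm, Section 5.3 says "Following each therapy session, participants will complete study surveys via REDcap and at 4 weeks following the intervention", and then "Participants will have up to 2 weeks to complete the follow-up questionnaires". It gives no minimum gap between a session and the survey. The usual care paragraph of the same section gives that arm educational materials and an identical survey schedule, with no session.

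**The concern.** Two features of the measurement differ from what a reader of Section 5.1 would expect.

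First, blinded assessment protects an endpoint when the blinded person produces the score. Here the child or parent produces it, and both know the arm. Knowledge of the arm can therefore enter every outcome, including both primary ones, whatever the assistant knows.

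Second, the setting in which the visit surveys are completed differs by arm. A CBT family may answer after a 60-minute session that teaches mindfulness and coping, while a usual care family answers with no such contact. Part of any difference at those visits could reflect the setting rather than a lasting change in itch or quality of life.

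The stake is interpretation. Section 2.0 expects to credit differences between the arms to the intervention, Aim 2 is framed as efficacy, and the data are meant to support a grant application. Section 5.4 promises CONSORT reporting, so the description of blinding will probably carry into the publication. Section 5.4 does not discuss expectancy or reporting bias and names no primary time point.

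**Working it through.** The plan gives no alpha, power, effect size or SD, so there is no figure of its own to reproduce. The main check sets the sections side by side.

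**Who produces the scores**

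| Item | Source | Content |
|---|---|---|
| Blinded | 5.1 | Research assistant only |
| Not blinded | 5.1; 5.3 Randomization | Therapists; families |
| Primary outcomes | 5.4 | NRS Itch Severity, CDLQI |
| Secondary outcomes | 5.4 | All other listed questionnaires |
| Instruments | Tables of Assessments | 12 child, 9 parent; none clinician-rated |
| Mode | 5.3, CBT arm | REDCap surveys |

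The NRS Itch Severity named in 5.4 does not appear in either table. The tables list an Itch Severity VAS, for child and for parent. Whichever scale is meant, the documents name no blinded rater for it. Parents review the sessions with the child and therapist, so the proxy ratings are unblinded too.

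**Which assessments follow a session in the CBT arm only**

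- Visits 2 and 3: dose VAS and itch VAS (child and parent), mood NRS (child), proxy itch short form (parent).
- Visit 4: these and the full battery, including the CDLQI. This is the only CDLQI between baseline and Follow-Up.
- Follow-Up: 4 weeks after the intervention, so no session comes just before it in either arm.
- Visit 1: unclear. Section 5.3 places the questionnaires after the clinic appointment. Section 1.0 places the first session directly after the clinic visit. The documents do not say which comes first.

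**Illustration of consequence (shift sizes assumed)**

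Inputs: 12 children per arm (Section 5.3: 24 dyads, 12 of them usual care, 1:1). Assumed: two-sided alpha of 5%, one two-sample t-test, no true effect, and a pure reporting shift of d SD favouring CBT.

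- Degrees of freedom = 12 + 12 - 2 = 22; critical t = 2.074.
- Noncentrality = d × √(n/2) = d × √6 = 2.449d.
- Rejection rate = P(T > 2.074) + P(T < -2.074), with T noncentral t.

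| Assumed shift (SD) | Noncentrality | Rejects, either direction | Rejects in favour of CBT |
|---|---|---|---|
| 0 | 0 | 5.0% | 2.5% |
| 0.25 | 0.612 | 9.0% | 8.5% |
| 0.50 | 1.225 | 21.6% | 21.5% |

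**The case against.** The strongest reply is that the protocol hides nothing. It states that therapists and participants are unblinded, its outcomes are plainly questionnaires, and it does not label the trial assessor-blinded. Families cannot be blinded to CBT versus handouts in a pilot of this kind. All of this stands, and it limits the point to accurate description and matched survey timing.

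Some stronger readings are tempting but are not supported.

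- A reader might infer that the assistant has no role. Section 5.1 gives the assistant a role in assessing and analysing outcomes with families. The role is under-described, not shown to be empty, and a blind on prompting, data handling and analysis has value even for self-report. How that blind survives contact with families who know their arm is not explained.
- A reader might infer that CBT families rate themselves immediately after a session with the therapist watching. The text says only "Following each therapy session, participants will complete study surveys via REDcap". It allows immediate completion but does not require it, and it does not say that the therapist is present or sees the answers.
- A reader might infer a momentary relaxation effect on both primary outcomes. Whether the CDLQI can carry one depends on its recall period, which the documents do not give. If the Visit 1 surveys also follow the first session, the CBT baseline could be lowered too, which would shrink the measured change. The net direction of the session-order effect is therefore not established.

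The objection that the 9% to 22% range is generic also stands. It would apply to any unblinded self-report trial with 12 per arm, and the planned analysis is a response profile over time, not a single t-test.

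**Conclusion.** The point holds in a limited form. The documents establish that all listed outcomes are self- or proxy-reported by families who know their arm, so the blinding in Section 5.1 does not extend to the ratings at any time point. They also establish that the CBT visit surveys come after a session, at an unspecified interval, and that the usual care surveys do not. The second feature can affect the Visit 2-4 itch and mood ratings and possibly the Visit 4 CDLQI. It does not affect the Follow-Up.

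The size of any bias is unknown. The rise from 5% to about 9% to 22% rests wholly on an assumed shift of 0.25 to 0.5 SD, an assumed 5% two-sided test and 12 per arm. It shows that a modest shift would matter at this sample size, not that one will occur. The change is worth making because it costs little.

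**What to change.** 1. In Section 5.1, replace the blinding sentence with a statement that children, parents and therapists are not blinded, that all outcomes are self- or proxy-reported, and that blinding applies only to the research assistant's data handling and analysis. Do not report the trial as having blinded outcome assessment.

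2. In Section 5.3 (CBT arm), change the survey timing:
   - Visits 2 and 3: REDCap sends the child and parent surveys automatically before the session, to be completed without the therapist. Usual care receives them on the same study days.
   - Visit 4: keep the survey after the last session, so that the end-of-treatment battery still reflects all four sessions. Send it after a fixed delay of some days, chosen by the sponsor and written into the protocol, and on the matching study day in usual care.
   - State in the same paragraph whether the Visit 1 surveys come before the first session.

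Cost: one corrected statement and a small change to REDCap scheduling. The downside is that the Visit 2 and 3 ratings each reflect one fewer session. The timing change does not remove expectancy, which is why the description in 5.1 must be corrected as well.

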## Brief Cognitive Behavioral Therapy to Treat Itch Rumination “Itch CBT” in Eczema

Patients are referred into this clinic through several “recruitment sites.” The diverse racial and ethnic demographics are summarized in Table I. The age group is chosen because all measures are validated in this age group, and cognitive interventions are easiest to implement in this narrow age group for a pilot study. Future work would expand to younger age groups.

**Table I.** Racial and Ethnic Demographics of Recruitment Sites

Recruitment Sites	African-American	Hispanic	Caucasian	Asian	Other
Clark-Deming Outpatient	36%	46%	15%	3%	<1%
Uptown Clinic	38%	35%	13%	9%	5%
La Rabida Hospital	74%	11%	8%	unknown	6%
Northbrook Lurie Outpatient	2%	7%	80%	6%	5%
Lurie Children's Outpatient	9%	23%	47%	4%	17%

A strength of this application is the volume and diversity of patients seeking treatment at the interdisciplinary pediatric allergy/dermatology clinic Lurie Children’s Hospital, allowing for a wide range of racial, ethnic, and socioeconomic diversity.

Participants in the active and control conditions will be matched for age, gender, and disease severity. All participants will be compensated \$25 for each visit for their time and to cover the cost of transportation. Inclusion and exclusion criteria are listed above in the previous section.

### 5.2 Aim 1 Study Design

#### Step 1: Conduct Qualitative Interviews to Develop Itch CBT

The CBT for itch rumination protocol and measure will be derived from qualitative (semi-structured) interviews with patients and families with AD from the interdisciplinary clinic at Ann & Robert H. Lurie Children’s Hospital, as well as via expert input from the study team. Qualitative interviews will be one-on-one with the patient and caregiver separately and will begin with open-ended questions to avoid biasing the participants with our own preconceptions of their needs. Example questions will include “When are you [your child] thinking about the itch most?” and “What would help take your mind off the itch?”. After open-ended questions, we will present participants with our conceptualization of itch rumination to ensure it accurately reflects their experiences, as well as questions adapted from the PCS-C for itch to determine whether these questions accurately reflect their experiences of itch rumination.

Participants will also be presented with various options and directed questions about their preferences for strategies to cope with itch rumination. Options for discussion will include behavioral strategies, such as pleasant activities to distract from the itch; cognitive interventions, such as self-questioning to de-escalate catastrophizing the itch (e.g. “The itching will never stop” and fears of the itch returning); and relaxation strategies, such as progressive muscle relaxation and diaphragmatic breathing when distraction is not possible, such as during the night. These strategies are the primary

## Brief Cognitive Behavioral Therapy to Treat Itch Rumination “Itch CBT” in Eczema

interventions of CBT and have been found particularly beneficial in treating physical difficulties, such as chronic pain .

For Aim 1, 20 patient-parent dyads (40 participants) of children with moderate/severe AD will be recruited for qualitative interviewing with a research assistant to provide feedback on the concept of itch rumination and therapeutic techniques to be included in CBT for itch rumination. Sample size for the interviews is based on our study team’s experience conducting qualitative research in support of protocol development and clinical health research. To ensure that qualitative findings are representative, research must 1) include key characteristics of the population thought to influence the outcomes of interest in the study sample; 2) confirm that the concepts are adequately described by study participants; and 3) bring participants into the study until no new themes, or relevant concepts, are obtained. This point of redundancy is known as theoretical saturation . It has been suggested that 20 patient-parent dyads is generally adequate to reach saturation .

